**Criteria for evaluation:**

Safety Endpoints:

Adverse events (AEs) reported by the subjects or observed during physical examination, vital signs assessment, electrocardiograms (ECGs) will be recorded by severity according to NCI CTCAE v5.0 and association with HBI-8000 and pembrolizumab will be assessed. Laboratory test results will be recorded and assessed against normal ranges. ECOG performance status will be monitored.

Efficacy Endpoints:

Target lesion(s) and non-target lesion(s) will be assessed by imaging studies at screening (baseline assessment), in the last week of Cycle 2 including C3D1, and then every 6 weeks ( $\pm 3$  days) thereafter. Tumor assessments will follow guidelines specified in RECIST criteria v1.1.

- ORR (complete response [CR]+partial response [PR])
- DCR (CR+PR+Stable disease [SD])
- DoR (Duration of response)
- PFS (Progression-Free Survival)

After the discontinuation of HBI-8000 treatment, subjects without disease progression will be followed for progression with imaging of measurable disease every 12 ( $\pm 1$ ) weeks until progression, initiation of another anti-cancer treatment, or referral to hospice whichever occurs first. Survival follow-up will be performed every 12 ( $\pm 1$ ) weeks by telephone contact or e-mail for up to 12 months after the last dose of HBI-8000.

**Statistical methods:**

General:

Statistical analyses will be performed using SAS® v9.4 or higher (SAS Institute, Cary NC, US). Statistical analyses of safety, tolerability and efficacy endpoints will be primarily descriptive in nature. Continuous variables will be summarized using descriptive statistics (n, mean, standard deviation, median, minimum, and maximum). Categorical variables will be summarized with the number and percentage (n, %) of subjects within each category. Time to event variables (i.e., PFS, DoR) will be analyzed using the Kaplan-Meier method. Where confidence limits are appropriate, the confidence level will be 95% (two sided), unless otherwise stated.

All subjects in the safety population (who received any amount of HBI-8000) will be included in the final summaries and listings of the safety data.

Sample Size Estimation:

Approximately 20 to 24 subjects are planned to be enrolled to characterize safety and allow for preliminary evaluation of efficacy endpoints in the specific patient population of interest.

Interim Analysis:

There will be no interim analysis for this Phase 2 study.

## **Schedule of Events (Dosing and Assessments)**

**Table 1: Schedule of Dosing and Assessments**

Visit	Screening	BL	Cycle 1	Cycle 2	Cycle 3	Cycle 4	≥Cycle 5	EoT Visit b	Survival F/U
Study Day	-28 to -1	-14 to -1	1	1 (±3d) a	1 (±3d)	1 (±3d)	1 (±3d)	30 days post dose b (±3d)	Every 12 Weeks (±1 week)
Informed consent c	X								
Inclusion/Exclusion Criteria	X	X							
Medical History, Baseline Signs and Symptoms, Cancer Diagnosis, and Treatment History d	X								
Demographics, height	X								
Vital signs e	X	X	X	X	X	X	X	X	
Physical exam, weight, ECOG Performance Status	X	X f	X	X	X	X	X	X	
ECG g		X						X	
Brain MRI h	X								
PD-L1 expression TPS i	X								
Hematology j		X	X	X	X	X	X	X	
Coagulation (PT/INR, aPTT)		X						X	
Serum chemistry k and LDH		X	X	X	X	X	X	X	
Urinalysis l		X						X	
Pregnancy test m		X						X	
Hepatitis B and C panel n	X								
HBI-8000 PO BIW o					X				
Pembrolizumab 200 mg infusion p OR Pembrolizumab 400 mg infusion p			X	X	X	X	X		
Tumor assessment q	X				Day 1 of Cycle 3, 5, 7, etc. (every 6 weeks ± 3 days)				
Adverse events r and SAE r				Continuous Assessment				X	
Concomitant medication	X	X		Continuous Assessment				X	
Treatment Compliance			X	X	X	X	X	X	

Visit	Screening	BL	Cycle 1	Cycle 2	Cycle 3	Cycle 4	≥Cycle 5	EoT Visit b	Survival F/U
Study Day	-28 to -1	-14 to -1	1	1 (±3d) a	1 (±3d)	1 (±3d)	1 (±3d)	30 days post dose b (±3d)	Every 12 Weeks (±1 week)
Survival s and Tumor Assessment F/U t									X

Abbreviations: ALT = alanine aminotransferase; aPTT = activated partial thromboplastin time; AST = aspartate aminotransferase; BIW = twice weekly; BL = baseline; BUN = blood urea nitrogen; CT = computed tomography; ECG = electrocardiogram; ECOG = Eastern Cooperative Oncology Group; eCRF = electronic Case Report Form; EoT = end of treatment; F/U = follow-up; HBsAg = hepatitis B surface antigen; INR = international normalized ratio; LDH = lactate dehydrogenase; MRI = magnetic resonance imaging; PO = by mouth; PD = progressive disease; PT = prothrombin time; TSH = thyroid stimulating hormone; T4 = thyroxine

- a. All visits and assessments from Cycle 2 onwards may be performed ± 3 days from the date of the projected visit.
- b. End-of-Treatment Safety Follow-Up visit, performed 30 ± 3 days after the last day of HBI-8000 administration, or before the initiation of new cancer treatment, whichever is earlier.
- c. Informed consent must be obtained prior to initiation of any study-specific procedures.
- d. Cancer diagnosis must include known mutation status for BRAF V600, EGFR, and ALK.
- e. Temperature, heart rate, diastolic and systolic blood pressure after subject is in a supine position for at least 5 minutes.
- f. Complete physical exam at baseline. Symptom directed physical exam for screening and all other cycles.
- g. Standard 12-lead ECG will be done using local standard procedures at Baseline and at End of Treatment Safety Follow-Up visits.
- h. MRI performed per institutional guidelines and practice, and if clinically indicated for subjects with documented brain metastasis.
- i. Historical data may be used to assess for eligibility. If historical data is not available, tumor tissue will be analyzed locally by an FDA-approved test to yield PD-L1 status prior to enrollment.
- j. Hematology panel to include hemoglobin, hematocrit, red blood cell count, white blood cell count, differential, platelet count.
- k. Chemistry panel to include BUN, creatinine, AST, ALT, LDH, total bilirubin (including direct fraction if total bilirubin abnormal), lipase, amylase, TSH, T4 free (direct), total protein, albumin, uric acid, alkaline phosphatase, sodium, potassium, calcium, magnesium, phosphorus, and glucose.
- l. Urinalysis: dipstick followed by microscopic examination, if abnormal results.
- m. For women of childbearing potential (including those with tubal ligation): Serum pregnancy test at baseline (within 14 days of starting treatment) and at the end of treatment.
- n. Hepatitis B and Hepatitis C testing to include HBsAg, anti-HCV antibodies.
- o. HBI-8000 should be administered twice a week approximately 30 minutes after a meal.
- p. Pembrolizumab 400 mg every 6 weeks or 200 mg every 3 weeks on Day 1 of each Cycle should be administered as intravenous (IV) infusion over 30 minutes and in accordance with the manufacturer package insert and institutional practice.
- q. Tumor assessment of all lesions by radiographic or other modality (CT, MRI). Tumor assessments to be performed at Screening, and Day 1 of Cycles 3, 5, 7, etc. every 6 weeks (± 3 days) thereafter until PD.
- r. Following the subject's written consent to participate in the study, all SAEs whether related or not related to study drug, must be collected, including those thought to be associated with protocol-specified procedures. Subjects with HBI-8000-related AEs of Grade ≥2 observed at the EoT visit should be followed-up and assessed monthly until the AEs have resolved to Grade ≤1 or are determined to be chronic or subject receives other anti-cancer therapy.
- s. Subject survival data will be collected by telephone contact or e-mail every 12 (±1) weeks after End-of-Treatment visit for up to 12 months after the last dose of HBI-8000 or until death.
- t. After discontinuation of HBI-8000 treatment, subjects without disease progression will be followed for progression with imaging of measurable disease every 12 (±1) weeks until progression, initiation of another anti-cancer treatment, or referral.

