### **3.1.2      Tumor Status and Survival Follow-Up**

Subjects without disease progression who completed up to 24 months of treatment or discontinued from HBI-8000 due to reasons other than PD are followed with imaging studies every 12 ( $\pm 1$ ) weeks until progression is documented, another anti-cancer treatment is initiated, or referral to hospice, whichever occurs first.

All subjects will be contacted approximately every 12 ( $\pm 1$ ) weeks by telephone contact or e-mail for survival follow-up for up to 12 months after the last dose of HBI-8000.

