#### **6.2.2.4.6 Follow-Up of Adverse Events**

Subjects should be asked to specifically describe any signs, symptoms, or AEs (regardless of relationship to Study Treatment) they may notice prior to the start of the study or thereafter. At a minimum, subjects should be asked to report any changes at each visit to the study center. Conditions that the subject experienced prior to informed consent should be recorded in the medical history section of the eCRF.

AEs, Grade 2 and above, considered to be at least possibly related to the Study Treatment must be followed up after the EoT assessment until the events have resolved, returned to the baseline level, are judged by the Investigator to be stable, or no longer require follow up provided the subject is withdrawn from the study due to initiation of new therapy or consent withdrawal for further follow-up. AEs that are assessed by the Investigator as unrelated to Study Treatment will be followed only to the EoT visit. The outcome of any AEs which do not resolve will be recorded as "ongoing" on the eCRF.

Serious adverse events (SAE) and adverse events of special interest (AESI), namely immune-related toxicities, will be collected for up to 90 days following cessation of treatment or 30 days following cessation of treatment if the subject initiates new anticancer therapy, whichever is earlier.

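### SAEs and immune-related AESIs are to be collected to day 90, but Table 1 schedules no AE/SAE enquiry covering all subjects after the day 30 ± 3 end-of-treatment visit

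*Combined protocol and SAP*

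**What the plan says.** **The collection rule.** Section 6.2.2.4.6 covers SAEs and "adverse events of special interest (AESI), namely immune-related toxicities". For these events the text reads "will be collected for up to 90 days following cessation of treatment", with 30 days applying instead to a subject who starts another cancer therapy.

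**The schedule.** The Table 1 row "Adverse events r and SAE r" shows continuous assessment on treatment, a mark at the EoT visit and nothing under Survival F/U. Footnote b describes the EoT visit as "performed 30 ± 3 days after the last day of HBI-8000 administration", or sooner if new cancer treatment begins. The Survival F/U column holds only survival and tumor assessment.

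**The calls.** Footnote s states: "Subject survival data will be collected by telephone contact or e-mail every 12 (±1) weeks after End-of-Treatment visit". Section 3.1.2 gives the same interval and then reads "weeks by telephone contact or e-mail for survival follow-up for up to 12 months after the last dose of HBI-8000". It ties the end of follow-up to the last dose but gives no start for the 12-week interval.

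**Other provisions after EoT.**
- Footnote r and Section 6.1.4 require monthly assessment of HBI-8000-related Grade ≥2 AEs seen at the EoT visit.
- Footnote t provides 12-weekly imaging for subjects without progression.
- Section 6.2.2.4.6 has subjects asked about changes whenever they visit the study center.
- Section 6.2.2.4.5 requires SAE reports within 24 hours of awareness.
- Section 4.4.1 mentions safety follow-up for subjects who withdraw from treatment only, without a schedule.

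**The concern.** A 90-day window for immune-related events is there to catch toxicity that appears after the EoT visit. That needs a point at which every subject still in the window is asked. Sections 6 and 6.3 make Table 1 the schedule that sites follow, and it contains no such point. A site can complete every scheduled contact for a subject and never ask about new events with onset after EoT.

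Safety is the first secondary objective (Section 2.2). The sponsor's safety committee reviews AESIs and SAEs (Section 6.3). Section 1.1.3.3 lists pneumonitis and interstitial lung disease among the important identified risks. The sample-size rationale in Section 7.1 is the probability of seeing at least one adverse event in 20 to 24 subjects, which presumes that events that occur are recorded. Missed late events can only lower the count.

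**Working it through.** The plan does not state the day of the first follow-up call, so there is no figure to reproduce. The check is calendar arithmetic, in days after the last HBI-8000 dose.

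**Inputs**
- Window closes: day 90 (Section 6.2.2.4.6), for subjects not starting new therapy.
- EoT visit: 30 ± 3, so day 27 to 33 (footnote b).
- Call interval: 12 ± 1 weeks, so 77 to 91 days (footnote s).

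**First call counted from the EoT visit (footnote s)**
- Earliest 27 + 77 = day 104; nominal 30 + 84 = day 114; latest 33 + 91 = day 124.
- Relative to day 90: 14, 24 and 34 days after the window closes.

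**First call counted from the last dose (a possible reading of Sections 3.1.2 and 6.2.1.1.2)**
- Day 77 to 91: between 13 days before and 1 day after the window closes. The call still asks only about survival.

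**Stretch with no scheduled all-subject AE/SAE enquiry**
- 90 − 33 = 57 days to 90 − 27 = 63 days, nominally 60.
- As a share of the window: 57/90 = 63% to 63/90 = 70%, nominally 60/90 = 67%. This is a share of days, not of events.

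**Who is reached in that stretch**
- *Subjects with a related Grade ≥2 AE at EoT:* monthly, near days 60 and 90 if a month is 30 days. The purpose is to follow a known event, but an assessment held at the center also brings the question about changes.
- *Non-progressed subjects:* imaging at about day 77 to 91 if counted from discontinuation. The question about changes applies if the scan is at the study center, which the documents do not say is always so.
- *Subjects continuing pembrolizumab after stopping HBI-8000 (Sections 3.1 and 4.5):* infusion attendances, with the same proviso.
- *Subjects who stopped for progression, have not started new therapy and have no footnote r event:* no scan, no visit and no safety question.

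**What under-recording could mean: an assumption, not an estimate.** Take a late-onset event with true incidence 10%, suppose all 20 to 24 subjects are in the unreached group, and let a fraction *a* of events be recorded. The probability of recording at least one is 1 − (1 − 0.10*a*)^n. The results match rows of Table 4:
- *a* = 1: 87.8% to 92.0% (10% row).
- *a* = 0.5: 64.2% to 70.8% (5% row).
- *a* = 0.1: 18.2% to 21.4% (1% row).

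The documents give neither *a* nor the size of the unreached group. Since some subjects are reached, the real loss at any given *a* is smaller than shown.

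**The case against.** The strongest reply is that safety follow-up does continue after EoT. Footnote r and Section 6.1.4 give monthly assessments to some subjects, and Section 6.2.2.4.6 requires a question about changes at every center visit, which can reach scan and infusion attendances. Section 4.4.1 mentions safety follow-up, and Section 6.2.2.4.5 obliges sites to report any SAE they learn of. This stands. A reader might infer from Table 1 that no subject has any safety contact after day 30, that late events surface only by chance, or that everyone who does not start new therapy is affected. The documents support none of these. The exposed group is narrower, and its size is not given. The reply does not supply an enquiry for that group: the 24-hour rule starts with awareness and does not create it, and Section 4.4.1 sets no timing.

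A second reply is that day 90 bounds when an event must begin, not when the site must hear of it, so a call at day 104 to 124 could still collect it. This also stands. The main omission is the safety question; the timing is secondary. But the call as specified collects survival data only.

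A third reply is that little analysis depends on these events. Section 7.5.2.1 closes the TEAE window 30 days after the last dose of any study treatment, and no separate late-event count is defined. That is correct, and it limits the effect to listings, the tabulations of SAEs and deaths, and committee review. A reader might also infer a demonstrated bias toward zero. The documents give no late-event rate, so only possible under-counting can be claimed.

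**Conclusion.** The point holds in a limited form. The plan sets a 90-day collection rule for SAEs and immune-related AESIs but schedules no enquiry covering all subjects after the EoT visit. For subjects outside the partial provisions, 57 to 63 days of the window rely on passive reporting. The first call is for survival only, whether it falls at day 104 to 124 (footnote s) or day 77 to 91 (counted from the last dose). Any error in the late SAE/AESI count is downward; its size cannot be derived from the documents.

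This rests on three assumptions: the AE/SAE row of Table 1 is blank under Survival F/U, as it reads in the available text; the 90 days run from the last HBI-8000 dose; and the subject has not started new anticancer therapy, in which case the window is 30 days. The second is not settled. Section 3.3 defines end of treatment by HBI-8000, Section 7.5.2.1 counts from the last dose of any study treatment, and Section 6.2.2.4.6 names no drug, while pembrolizumab may continue alone. The primary ORR analysis is unaffected.

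**What to change.** - Make the first follow-up call a safety and survival contact at day 90 (+7 days). Ask about SAEs and AESIs with onset since the EoT visit and up to day 90. Continue 12-weekly survival calls from there. The look-back then runs from 90 − 33 = 57 to 97 − 27 = 70 days, against 77 to 91 days under footnote s.
- Mark this contact in the AE/SAE row of Table 1 and align footnote s with Sections 3.1.2, 6.1.5 and 6.2.1.1.2 on where the 12-week interval starts.
- State in Section 6.2.2.4.6 whether cessation of treatment means the last dose of HBI-8000 or of either study drug, and time the contact from that date.
- Tabulate SAEs and AESIs with onset on days 31 to 90 separately, since they fall outside the TEAE tables.

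The cost is one re-timed call with a short added question, or at most one extra short call for each of 24 or fewer subjects, plus one small table. No clinic visit is added.

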## LIST OF ABBREVIATIONS

Abbreviation	Definition
ADL	Activities of daily living
AE	Adverse event
AESI	Adverse event of special interest
ALK	Anaplastic lymphoma kinase
ALT	Alanine aminotransferase
aPTT	Activated partial thromboplastin time
AST	Aspartate aminotransferase
ATC	Anatomical therapeutic chemical classification system
ATL	Adult T-cell leukemia/lymphoma
AUC	Area under the curve
BIW	Twice a week
BRAF	B-Raf proto-oncogene, serine/threonine kinase gene
BUN	Blood urea nitrogen
C1D1	Cycle 1 Day 1
CFR	Code of Federal Regulations
COVID-19	Coronavirus disease 2019
CPI	Checkpoint inhibitor
CR	Complete response
CRO	Contract research organization
CT	Computerized tomography
CTCAE	Common Terminology Criteria for Adverse Events
CTL	Cytotoxic T lymphocyte
CYP	Cytochrome P450
DBP	Diastolic blood pressure
DCR	Disease control rate
DNA	Deoxyribonucleic acid
DoR	Duration of response
ECG	Electrocardiogram
ECOG	Eastern Cooperative Oncology Group

Abbreviation	Definition
eCRF	Electronic Case Report Form
EDC	Electronic data capture
EGFR	Epidermal growth factor receptor
EoT	End-of-treatment
ESF	Eligibility Screening Form
FAS	Full analysis set
FDA	Food and Drug Administration (US)
GCP	Good clinical practice
G-CSF	Granulocyte-colony stimulating factor
HBVsAg	Hepatitis B surface antigen
HCV	Hepatitis C virus
HDAC	Histone deacetylase
HDACi	Histone deacetylase inhibitor
HDPE	High-density polyethylene
HEENT	Head, eye, ear, nose, and throat
HIV	Human immunodeficiency virus
HR	Hazard ratio
HUYABIO	HUYABIO International LLC
IC 50	50% inhibitory concentration
ICF	Informed consent form
ICH	International Council for Harmonisation
IEC	Independent Ethics Committee
IgG	Immunoglobulin G
INR	International normalized ratio
IP	Investigational Product
irAE	Immune-related Adverse Event
IRB	Institutional Review Board
IV	Intravenous
LAR	Legally authorized representative
LDH	Lactate dehydrogenase

Abbreviation	Definition
MDSC	Myeloid-derived suppressor cells
MedDRA	Medical Dictionary for Regulatory Activities
MRI	Magnetic resonance imaging
MTD	Maximum tolerated dose
NCI	National Cancer Institute
NE	Not evaluable
NK	Natural killer
NSCLC	Non-small cell lung cancer
ORR	Objective Response Rate
OS	Overall survival
PD	Progressive disease
PD-1	Programmed cell death protein 1
PD-L1	Programmed death-ligand 1
PFS	Progression-Free Survival
PPS	Per-Protocol Set
PR	Partial response
PSA	Prostate specific antigen
PSRMC	Product Safety and Risk Management Committee
PT	Prothrombin time
PTCL	Peripheral T-cell lymphoma
Q2W	Every two weeks
QTc	QT interval corrected by heart rate
QTcF	QT interval corrected by heart rate using Fridericia's correction formula
RBC	Red blood cell
RCC	renal cell carcinoma
RECIST	Response Evaluation Criteria in Solid Tumors
RENCA	Renal adenocarcinoma
RNA	Ribonucleic acid
ROS	c-ros oncogene
RP2D	Recommended Phase 2 dose

Abbreviation	Definition
SAE	Serious adverse event
SAP	Statistical Analysis Plan
SBP	Systolic blood pressure
SD	Stable disease
SOP	Standard operating procedure
STD	Sum of target lesion(s) diameter(s)
SUSAR	Suspected unexpected serious adverse drug reaction
T4	Thyroxine
TEAE	Treatment-emergent adverse event
TIW	Three times a week
T Reg	Regulatory T-cell
TSH	Thyroid stimulating hormone
ULN	Upper limit of normal
US	United States (of America)
USP	United States Pharmacopeia
USPI	US package insert
WBC	White blood cell
WHO	World Health Organization
WHO DDE	World Health Organization drug dictionary enhanced

## 1 BACKGROUND

### 1.1 Introduction

HBI-8000 (chidamide, tucidinostat) is an orally bioavailable inhibitor, selective for cancer-associated histone deacetylase (HDAC) isoenzymes 1, 2, 3, and 10. By affecting the acetylation of histones and non-histones in cancerous and immune cells, it regulates the gene expression epigenetically without changing the DNA sequence and modulates immune functions and malignant phenotypes. Selective HDAC inhibitors (HDACi) such as HBI-8000 have been shown to alter the expression of genes which are aberrant, silenced or overexpressed in cancer cells. HUYABIO International, LLC (HUYABIO) is developing HBI-8000 as a monotherapy for the treatment of hematological malignancies and in combinations for the treatment of solid tumors such as melanoma, breast, kidney, and lung cancers. Combination regimens of HDACi with other cancer drugs have shown synergistic effects both in pre-clinical and clinical studies. At the same time, these combinations have enhanced the efficacy, reduced the toxicity and tumor resistance to therapy [Hontecillas-Prieto 2020].

Programmed cell death protein (PD-1) and its ligands (PD-1/PD-L1 axis) play a fundamental role in the evasion of tumor cells from antitumor immunity. The safety and efficacy of HBI-8000 in combination with nivolumab, an inhibitor to PD-1/PD-L1 axis, has been evaluated in a Phase 1b/2 study (HBI-8000-302) in patients with advanced melanoma, renal cell carcinoma (RCC) and non-small cell lung cancer (NSCLC). Interim results from the Phase 1b part of the study established that HBI-8000, 30 mg twice weekly in combination with the standard dose of nivolumab was well tolerated. The tolerability was further confirmed in the expanded cohorts in Phase 2. Efficacy signals were also observed throughout this study, including patients with NSCLC regardless of their prior exposure to immune checkpoint inhibitor(s).

The hypothesis is that HBI-8000, combined with approved immune checkpoint inhibitors can improve the antitumor immune response in cancer patients, possibly by enhancing tumor immunogenicity and inflammatory response in tumor microenvironment. In the present study, the safety and efficacy of HBI-8000 in combination with KEYTRUDA® (pembrolizumab) in advanced and metastatic NSCLC will be explored. Efficacy will be assessed based on objective response rate (ORR), progression-free survival (PFS), and duration of response (DoR).

